5.4 Other Secondary Endpoints

5.4.1 Definitions

CRS (As observed)

The CRS defined for the primary analysis is derived based on a combination of the hospitalization and oxygen supplementation status of the participant. More specifically, the status is considered as the status in which the participant would have been, according to the investigator, in case all circumstances were optimal. As an alternative measure, the CRS (As observed) will be derived using only the information on the actual status of the participant, ignoring alternative choices made because of lack of resources, participants choice and others.

Similar as for the derivation of the CRS, a participant will be evaluated in the same ordering of the categories as below. Once a participant fulfils the criteria for a category, the category is assigned to the participant and the evaluation stops. The actual hospitalization status will be considered in this derivation.

- **Score 6:** Based on the status of the participant on the day of the assessment (based on the date of death).

Based on Type of Oxygen Supplementation page:

- **Score 5:** At least one of the following scores is ticked:
 - IMV
 - Extra Corporeal Membrane Oxygenation
- **Score 4:**
 - Non-invasive mechanical ventilation (CPAP or BIPAP), high-flow nasal cannula, non-rebreather device or OxyMask is used at any time on the day, OR
- **Score 3:**
 - Receiving supplemental oxygen through a face mask, nasal cannula or other
- **Score 2:**
 - Hospitalized as reported
- **Score 1:**
 - Not hospitalized as reported: a distinction will be made between subjects discharged and in need of (score 1.2) or not in need of (score 1.1) oxygen supplementation as indicated by the investigator on the discharge questionnaire. This distinction will not be made when calculating improvements on the CRS (As observed), for which score 1 will be used in both cases.

Further Definitions for Other Secondary Endpoint

Formulae to be used for derived variables, including data conversions, are provided in the tables below.

| Measurement | Formula/Definition |
|--|--|
| Time to sustained improvement of at least 1 category relative to baseline on the 6-point ordinal CRS (up to Day 28) (days) [Time-to event] | 
Similar as for the primary endpoint, but with an improvement of 1 category (instead of 2 categories).
 
The parameter name for the analysis will be "Time to sustained improvement with at least 1 category on the CRS"
 |
| Time to sustained improvement of at least 2 categories relative to baseline on the CRS (As observed) (up to Day 28) (days) [Time-to event] | 
Similar as for the primary endpoint, but with an improvement of at least 2 categories on the CRS (As observed).
 
The parameter name for the analysis will be "Time to sustained improvement with at least 2 categories on the CRS (As observed)"
 |
| Time from study intervention to end of oxygen supplementation (up to Day 28) (days) [Time-to event] | 
The event of end of oxygen supplementation is obtained when a participant reaches a CRS score of 2 or 1.1, provided the event is not followed by a documented deterioration* up to and including day 28 or until trial discontinuation, whichever comes first.
 
Participants who are discharged from hospital but reported as still in need of supplemental oxygen (score 1.2) will be censored on the day after hospital discharge, unless they die at or before day 28.
 
Participants who discharge on score 1.2 and die at or before day 28 will be censored on day 28.
 
Participants who are still hospitalized and on oxygen at day 28 will be censored on day 28.
 
Participants who discontinue the trial before day 28 while still on oxygen will be censored on the day of discontinuation.
 
* In the context of this endpoint, a score of 3,4,5,6 would imply a deterioration with respect to the event.
 
The parameter name for the analysis will be "Time to end of oxygen supplementation (up to Day 28) (days)"
 |
| Time from study intervention to hospital discharge (up to Day 28) (days) [Time-to event] | 
Similar as for the primary endpoint, but with a score of 1.1 or 1.2 on the CRS (instead of an improvement of 2 categories).
 
The parameter name for the analysis will be "Time to discharge (or readiness to discharge) to home (up to day 28)"
 |

| | |
|---|---|
| Time from study intervention to hospital discharge (up to Day 28) (days) among the surviving participants [Time-to event] | Similar as for the primary endpoint, but with a score of 1.1 or 1.2 on the CRS (instead of an improvement of 2 categories). This endpoint will be evaluated in the subgroup of participants who were still alive at day 28. |
| Time to Mechanical Ventilation (up to Day 28) (days) among participants not on mechanical ventilation at Baseline [Time-to event] | Similar as for the primary endpoint, but with a score of 5 on the CRS (instead of an improvement of 2 categories). Participants who did not evolve to score 5 and who die will be censored at the day of death. This endpoint will be evaluated in the subgroup of participants for which the CRS is less than 5 at Baseline. |
| Time from study intervention to ICU discharge (up to Day 28) among the participants on ICU at baseline (days) [Time-to event] | Subjects who die at or before day 28 will be censored on day 28. Subjects alive on day 28: Only ICU periods with a starting day \leq day 28 are taken into account. Missing end dates of ICU periods are imputed with the cut-off date (for ongoing subjects) or the date of study discontinuation/completion - If last ICU stay end date $<$ minimum(date visit day 28, study discontinuation, study completion), -> the subject has an event on the last day in the ICU + 1 day. - If last ICU stay end date \geq minimum (date visit day 28, study discontinuation, study completion), -> the subject will be censored on minimum(day 28, day study discontinuation, day study completion). |
| Total length of hospitalization among the surviving participants (up to Day 28) (days) [Duration] | The total number of days a subject stayed in the hospital during the period from study drug intake until day 28, calculated as sum of the individual hospitalization periods, including re-hospitalizations. This endpoint will be evaluated in the subgroup of participants who were still alive at day 28 The total length of hospitalization will be missing for participants who discontinue the trial for other reason than death before day 28. |
| Number of ventilation free days in participants on IMV/ECMO at baseline (up to Day 28) (days) [Duration] | Calculated as: Date day 28 – maximum date of day with score ≥ 5 Participants who die will be considered as being on IMV/ECMO until day 28. |

| | |
|---|--|
| Improvement at day 28 on the CRS with at least 1 category at day 28 (or at discharge/discontinuation) [Incidence] | CRS improved with at least 1 category at day 28 (or at discharge/discontinuation) when compared to baseline (Yes/No) |
| Improvement at day 28 on the CRS (As observed) with at least 2 categories at day 28 (or at discharge/discontinuation) [Incidence] | The CRS (As observed) improved with at least 2 categories at day 28 (or at discharge/discontinuation) when compared to baseline (Yes/No) |
| CRS worsening relative to Baseline (up to Day 28) [Incidence] | CRS worsened with at least 1 category between day 5 and day 28 (Yes/No) |
| Ventilation free survival at Day of Discharge/Day 28 [Incidence] | CRS score 1, 2, 3 or 4 at Day 28. Participants with a missing score at Day 28 will not be considered |
| CRS at Day 7, 14, 21 and 28 [Proportions] | See section 5.2.1. |

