1.3. Schedule of Activities (SoA)

Safety laboratory testing (hematology, chemistry, and coagulation tests) will routinely be performed by local laboratories (refer to Section 10.2 Appendix 2: Clinical Laboratory Tests and Section 10.3 Appendix 3: Clinical and Laboratory Assessments Described per Day).

	Screening Phase ^a	Phase Day 1 to Day 28			Post Day 28 Follow-up Phone Calls	
Day	Screening	Baseline ^a Day 1	Day 2 to Day 28 ^b or day of discharge from hospital ^{aa} , or study discontinuation, whichever comes first	Day 28 Visit if discharged earlier (Phone Call) Day 28 ±3 days	Day 56, Day 84, Day 112 ±7 days	
Week	Week 1	Week 1 (Day 2) to Week 4			Week 4	Week 8, 12, 16
General Screening/Baseline assessments						
ICF ^c	X					
Inclusion/exclusion criteria	X	X ^d				
Demographics, medical history ^c	X					
Targeted physical exam ^b	X		Any clinically significant findings to be reported			
Treatment administration						
Randomization ⁱ		X				
Administration of study intervention ⁱ		X				
Concomitant medication						
Concomitant medication recording	X	X	Throughout the study	X ⁿ	X ⁿ	
Respiratory function related assessments						
Type of supplemental oxygen	X	X	Once per day			
Resting SpO ₂ , FiO ₂ (if any) ^j	X	X	Minimum 4 times per day			
Arterial pH, PaO ₂ , PaCO ₂ ^j			As available			
Level of consciousness (Glasgow coma scale score) ^k	X	X	Once per day while in the ICU			
Pulmonary X-ray (or CT imaging or lung ultrasound if X-ray not available)	X ^{g,bb}		As per SOC, report upon worsening and last available			

	Screening Phase ^a	Phase Day 1 to Day 28				Post Day 28 Follow-up Phone Calls	
Day	Screening	Baseline ^a Day 1	Day 2 to Day 28 ^b or day of discharge from hospital ^{aa} , or study discontinuation, whichever comes first		Day 28 Visit if discharged earlier (Phone Call) Day 28 ±3 days	Day 56, Day 84, Day 112 ±7 days	
Week	Week 1		Week 1 (Day 2) to Week 4			Week 4	Week 8, 12, 16
General safety related assessments							
Standard 12-lead ECG	X ^{g,bb}		one ECG is to be taken between Day 4 and Day 8				
Vital signs (body temperature, pulse, SBP/DBP, respiratory rate)	X	X	As per SOC, minimum 4 times per day while in the ICU, afterwards once per day				
Any AE	X	X	Throughout the study				X ⁿ
Record discharge from ICU, discharge from hospital			As applicable				
Safety laboratory assessments^{dd}							
Hematology ^l	X ^g	X	Day 3, Day 7, Day 14, Day 21, Day 28 ^{cc}				
Chemistry ^l general safety	X ^g	X	Day 3, Day 7, Day 14, Day 21, Day 28 ^{cc}				

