Self-reported oxygen needed (yes/no)					X ⁿ	X ⁿ		
Self-reported pregnancy status					X ⁿ	X ⁿ		
Record readmission(s) post discharge and reason					X ⁿ	X ⁿ		

- Laboratory testing to be performed centrally

Note: If multiple assessments are scheduled for the same timepoint, it is recommended that procedures be performed in the following sequence: ECG, oxygen saturation, vital signs, blood sampling.

Abbreviations: AE: adverse event, AESI: adverse event of special interest; aPPT: activated partial thromboplastin time; CRP: C-reactive protein; CT: computed tomography; DBP: diastolic blood pressure; FiO₂: percentage of inspired oxygen; ECG: electrocardiogram; HDL: low-density lipoprotein; ICF: informed consent form; ICU: intensive care unit; INR: international normalized ratio; LDL: low-density lipoprotein; PaCO₂: partial pressure of carbon dioxide in arterial blood; PaO₂: partial pressures of oxygen in arterial blood; PCR: polymerase chain reaction; PT: prothrombin time; SAE: serious adverse event; SBP: systolic blood pressure; SOC: standard of care; SpO₂: peripheral capillary oxygen saturation.

Footnotes:

- a. Screening assessments start after signing of the ICF and can continue on the next calendar day, if needed. All screening and baseline assessments may also take place on the same day. Screening/Baseline assessments required to verify study eligibility and data collection for assessment of the 6-point ordinal clinical recovery category should take place prior to randomization. All Screening/Baseline procedures should take place prior to study drug administration.
- b. The assessment schedule will be on a weekly basis for participants still hospitalized after Day 28. For the required assessments, refer to Section [10.3, Appendix 3: Clinical and Laboratory Assessments Described per Day](#).
- c. Consent to be obtained before the first study-related activity. An exception is in the case of an emergency enrollment in which the informed consent can be obtained as soon as possible.
- d. If a participant's clinical status changes after screening but before randomization such that he or she no longer meets all eligibility criteria, then the participant should be excluded from participation in the study.
- e. Medical history should include collecting onset of COVID-19 symptoms, prior therapy, and date of SARS-CoV-2 diagnosis if available.
- f. A urine pregnancy test is to be performed in women of childbearing potential only.

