8.2.7. Self-reported Oxygen Need

On the Day 28 phone call visit (if discharged before Day 28) and during the post Day 28 follow-up phase (phone call visits) participants will be asked whether they require supplemental oxygen (yes or no). The results should be documented in the eCRF.

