 - o A distinction will be made between subjects discharged and in need of (score 1.2) or not in need of (score 1.1) oxygen supplementation as indicated by the investigator on the discharge questionnaire. This distinction will not be made when calculating improvements on the CRS, for which score 1 will be used in both cases.

Hospitalization status

The hospitalization status considered for the definition of the CSR will be defined according to the rules described below. The hospitalization status will be evaluated in the same ordering of rules. Once a participant fulfils the criteria, the hospitalization status is defined and the evaluation stops.

1. If a participant is discharged to the alternate care settings ‘different hospital’, ‘acute care facility’, ‘subacute care facility’ or ‘hospice/palliative discharge’, the participant will be considered hospitalized until day 28 or trial discontinuation, whichever comes first. The participant will be categorized in the category the participant was in at time of discharge until trial discontinuation.
2. If a participant is discharged ‘against medical advice’, the participant will be considered hospitalized on the day of discharge and on the day after discharge, unless the participant discontinued the trial. The participant will be categorized in the category the participant was in at time of discharge. The CRS will be considered missing from 2 days after discharge onwards.
3. If a participant is hospitalized although ‘ready for discharge’ according to the investigator, the participant will be considered hospitalized up to and including the first day on which the participant was considered ready for discharge. The participant will be considered “Not hospitalized” from the day after until day 28 or trial discontinuation, whichever comes first (unless the status changes back to “not ready for discharge”).
4. If a participant is discharged although ‘not ready for discharge’ according to the investigator, the participant will be considered hospitalized up to and including 1 day

after the day of discharge, unless the participant discontinued the trial. The participant will be categorized in the category the participant was in at time of discharge. The participant will be considered non hospitalized from 2 days after the day of discharge onwards until day 28 or trial discontinuation, whichever comes first.

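### Time to end of oxygen supplementation: living participants sent home on oxygen are censored the day after discharge although the Day 28 call records their oxygen status, which biases the comparison if the arms differ in discharge on oxygen

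*SAP*

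**What the plan says.** SAP 5.4.1 counts the event when a participant "reaches a CRS score of 2 or 1.1, provided the event is not followed by a documented deterioration". Score 1.2 (discharged, still needing oxygen) is never an event. The 1.1/1.2 split reflects need of "oxygen supplementation as indicated by the investigator on the discharge questionnaire" (SAP 5.2.1), so it is fixed at discharge.

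The same SAP row gives three rules for people not known to have stopped oxygen:

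- Discharged with score 1.2 and alive at Day 28: "will be censored on the day after hospital discharge, unless they die at or before day 28".
- Discharged with score 1.2 and dead by Day 28: "Participants who discharge on score 1.2 and die at or before day 28 will be censored on day 28".
- Still an inpatient on oxygen: "Participants who are still hospitalized and on oxygen at day 28 will be censored on day 28".

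Protocol 8.2.7 states that on the Day 28 call, for those discharged earlier, "participants will be asked whether they require supplemental oxygen (yes or no". The Schedule of Activities lists the item and gives the contact as "Day 28 Visit if discharged earlier (Phone Call) Day 28 ±3 days". The SAP does not use the answer for this endpoint and gives no sensitivity analysis for it. SAP 5.4.2 tests the endpoint with a stratified log-rank test, 1-sided at 5%, and presents Kaplan-Meier proportions.

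**The concern.** Log-rank and Kaplan-Meier methods treat a censored participant as having the same future chance of the event as those left in the risk set. Here censoring is triggered by the outcome state itself, being on oxygen at discharge, and its date depends on later survival. The group removed is well enough to go home but not yet off oxygen. Nothing in the documents suggests that they would stop oxygen at the same rate as inpatients on oxygen.

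If one arm sends more people home on oxygen, the distortion differs between arms. When most of them stay on oxygen to Day 28, removing them flatters that arm. When most stop at home, their events are lost and that arm is penalised.

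**Working it through.** **Inputs from the documents.** Arm sizes 74 and 37. The primary-endpoint design model (SAP 1.4) has lognormal times, medians of 28 and 16.8 days, log-scale SD 0.9, and mortality of 40% and 20%.

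**Inputs assumed.** The share sent home on oxygen in each arm, and how many of those stop oxygen by Day 28. The documents give neither. Where deaths occur below, they are held at risk to Day 28, as SAP 5.2.3 does for the primary endpoint.

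**1. The plan's own figure.** The documents give no power or effect for this endpoint, so the primary design serves only to anchor the model. Simulating it at 111 participants with an unstratified log-rank test, 2-sided 5%, gives power of 0.81 to 0.83. This agrees with the stated 80% or more.

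**2. Hand example: all home-oxygen participants still on oxygen at Day 28.** No deaths. Home-oxygen participants leave on Day 8 and are censored on Day 9. In-hospital stops are spread evenly over Days 6 to 26.

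- Sirukumab: 34 of 74 stop oxygen and 20 go home on it. Six stops fall by Day 9, leaving 74 − 6 − 20 = 48 at risk, of whom 28 stop. SAP rule: 1 − (68/74) × (20/48) = 61.7%.
- Control: 19 of 37 stop and 2 go home on oxygen. Four stops fall by Day 9, leaving 37 − 4 − 2 = 31 at risk, of whom 15 stop. SAP rule: 1 − (33/37) × (16/31) = 54.0%.
- Keeping everyone at risk to Day 28: 34/74 = 45.9% and 19/37 = 51.4%.

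The hazard ratio is 1.19 under the SAP rule and 0.86 when the Day 28 status is used. Neither is significant (1-sided p 0.271 and 0.700). With a smaller true gap (34/74 = 45.9% against 18/37 = 48.6%, 2 control participants sent home), the SAP hazard ratio is 0.99 with 8 of 74 sent home on oxygen and 1.03 with 10 of 74. That is 13.5% against 2/37 = 5.4%.

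**3. Varying how many stop at home.** Assume 20% die and survivors in hospital have a daily chance of 0.03 of stopping oxygen. The daily chance of discharge on oxygen is 0.02 in arm A and 0.005 in arm B.

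- Sent home on oxygen: A 0.8 × (0.02/0.05) × (1 − 0.95^28) = 24.4%; B 0.8 × (0.005/0.035) × (1 − 0.965^28) = 7.2%.
- Stopped in hospital: A 0.8 × (0.03/0.05) × (1 − 0.95^28) = 36.6%; B 0.8 × (0.03/0.035) × (1 − 0.965^28) = 43.3%.
- True proportion off oxygen = stopped in hospital + (1 − k) × sent home, where k is the share of the home group still on oxygen at Day 28.
- SAP rule: 1 − Π[1 − 0.03 s/(s + 0.2)] over 28 days, where s = 0.8 × 0.95^(t−1) for A and 0.8 × 0.965^(t−1) for B. This gives 42.9% and 45.2%, a difference of −2.3 points whatever k is.

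| k | True A | True B | True difference | SAP difference |
|---|---|---|---|---|
| 0.4 | 51.2% | 47.6% | +3.6 | −2.3 |
| 0.6 | 46.3% | 46.2% | +0.1 | −2.3 |
| 0.8 | 41.5% | 44.7% | −3.2 | −2.3 |
| 1.0 | 36.6% | 43.3% | −6.7 | −2.3 |

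The sign changes clearly at k = 0.4. At 0.8 and above there is no reversal, and the rule understates arm A's deficit.

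**4. Hazard ratio and test.** Lognormal simulation with SD 0.9 and 74:37 allocation. Shares are sirukumab against control.

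- Equal shares of 10%: hazard ratio 1.00 under no effect; 2.43 becomes 2.47 under the design effect.
- No effect, home group all still on oxygen at Day 28, shares 50% against 10%: SAP hazard ratio 1.11; 1-sided rejection 9.1% against 4.5% with full data.
- True hazard ratio 1.32, home group all off oxygen by Day 28: SAP hazard ratio 1.07 at 30% against 10%, and 0.79 at 50% against 10%.
- Design-size effect (about 2.4), home group all off oxygen by Day 28: 1.97 at 30% against 10%, with power falling from 0.89 to 0.63. It drops below 1 (0.92) only at 70% against 10%.

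**5. Using the Day 28 answer.** In the case with true hazard ratio 1.32 and shares of 50% against 10%, placing home stops at the midpoint between discharge and Day 28 gives 1.27. Placing them all on Day 28 gives 1.11. Both restore the direction, but the midpoint loses much less.

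**The case against.** The strongest defence is that the rule is pre-specified and censors at the last status recorded on the scale. The call item is self-reported, has a window of ±3 days, sits under safety assessments and gives no stop date. It therefore cannot supply an exact event time. That stands, and it shapes the fix. It does not justify discarding a known status, and a yes answer needs no stop date at all.

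A reader might infer that the rule will reverse the comparison, or that it favours sirukumab. The documents support neither. They give no rate of discharge on oxygen, no difference between arms and no rate of stopping at home, and the trial is blinded. Reversal appears only under chosen imbalances with small to modest true effects, and the bias can run either way.

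Sampling error also matters. In simulated 74:37 trials of essentially the step 3 setting with k = 0.4, the arm difference had an SD of about 10 points, against an expected shift of about 6 points (+3.3 to −2.8). Mean log-rank Z was −0.25 under the SAP rule and +0.07 with home stops placed on Day 28.

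The consequence is limited. This is an other secondary endpoint outside the testing hierarchy, and the time-to-discharge endpoints count 1.1 and 1.2 alike as events.

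**Conclusion.** The point holds in conditional form. The censoring is informative on the face of the SAP, and participants on oxygen are handled differently according to where they are and whether they later die. Bias between arms arises if discharge on oxygen differs by arm. It is negligible for the hazard ratio when shares are equal. Under the assumed imbalances it ranges from dilution of a large effect (about 2.4 to 1.97) to a change of sign for a modest one (1.32 to 0.79). The sign can change only with a marked imbalance and a small to modest true effect, and all these shares are assumptions.

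The primary endpoint pools scores 1.1 and 1.2 and is unaffected. The change should be made because it needs no new data, but the trial's main conclusion does not depend on it.

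**What to change.** Amend the SAP 5.4.1 row for participants discharged with score 1.2 and alive at Day 28:

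- Oxygen still needed at the Day 28 call: censor at Day 28, as for those still in hospital on oxygen.
- Oxygen no longer needed: count an event, interval-censored between discharge and the call. Use an interval-censored method or the midpoint in the main analysis, and placement on Day 28 as a sensitivity analysis.
- Call missing: censor the day after discharge, as now.

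Keep the current rule as a further sensitivity analysis, and tabulate discharge on oxygen by arm so that any imbalance is visible.

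The cost is SAP wording and programming with an item already collected. The downside is a stop date that is approximate and rests on self-report within ±3 days of Day 28.

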5.2 Primary Efficacy Endpoint(s)

5.2.1 Definitions

Six-point ordinal clinical recovery scale

The 6-point ordinal clinical recovery scale (CRS) provides 6 mutually exclusive conditions ordered from best to worst, and the score reflects the participant's worst situation on the day of the assessment:

1. Not hospitalized
2. Hospitalized, not requiring supplemental oxygen
3. Hospitalized, requiring low flow supplemental oxygen
4. Hospitalized, on non-invasive ventilation, nonrebreather mask or high flow oxygen device
5. Hospitalized, on IMV or ECMO
6. Death

The CRS can be derived from baseline up to and including day 28. The CRS will be missing after trial discontinuation if the participant discontinued the trial for other reason than death. Participants who die before day 28 (before or after discharge from hospital) will be considered to continue the trial up to and including day 28.

The CRS categories are defined below. For ease of categorization, the categories are defined from worst to best. A participant will be evaluated in the same ordering of the categories as below. Once a participant fulfils the criteria for a category, the category is assigned to the participant and the evaluation stops.

6. Death
 - o Participant died at any time on the day of assessment or earlier (all-cause mortality).
5. Hospitalized, on IMV or ECMO

- o IMV or ECMO is used at any time on the day of assessment, OR
- o From a Medical Perspective, the participant should have been on IMV on the day of the assessment

4. Hospitalized, on non-invasive ventilation, nonrebreather mask, or high flow oxygen device
 - o The participant is on supplemental oxygen and the worst FiO₂ is $\geq 50\%$.
3. Hospitalized, requiring low flow supplemental oxygen
 - o On supplemental oxygen with worst FiO₂ $< 50\%$ and the participant was not able to sustain a blood oxygen saturation of $> 93\%$ when breathing room air, OR
 - o Not on supplemental oxygen and the minimum of all available SpO₂ values during the day is $\leq 93\%$
2. Hospitalization, not requiring supplemental oxygen
 - o Hospitalized according to the status described below
1. Not hospitalized, including subjects on low level of oxygen

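### Time to end of oxygen supplementation: a survivor who scores 2 in hospital and is discharged on oxygen (score 1.2) meets both the event rule and a censoring rule, and the SAP does not say which prevails

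*SAP*

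**What the plan says.** The endpoint is defined in the table of other secondary endpoints in SAP 5.4.1. A participant has the event when he or she "reaches a CRS score of 2 or 1.1, provided the event is not followed by a documented deterioration" up to Day 28 or trial discontinuation. The footnote to that entry reads "In the context of this endpoint, a score of 3,4,5,6 would imply a deterioration with respect to the event".

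The next sentence of the entry deals with discharge on oxygen: participants "reported as still in need of supplemental oxygen (score 1.2) will be censored on the day after hospital discharge". Its only exception is death by Day 28, and those who die are censored at Day 28 instead.

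The two versions of score 1 come from SAP 5.2.1: "A distinction will be made between subjects discharged and in need of (score 1.2) or not in need of (score 1.1) oxygen supplementation", as recorded by the investigator on the discharge questionnaire. Under hospitalization rule 5 in the same section, the day of discharge keeps the in-hospital category and the not-hospitalized score begins the next day.

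SAP 5.4.2 tests the time-to-event secondary endpoints with a log-rank test stratified by age and invasive ventilation, 1-sided at 5%, in both the Primary and the ITT analysis sets.

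**The concern.** Score 1.2 is deliberately left out of the event scores, because that person still needs oxygen. It is also left out of the list of scores that cancel an event. The event rule therefore takes no notice of 1.2 when it follows a 2, while a separate sentence instructs the analyst to censor that same person.

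Two programmers following the SAP faithfully could build different datasets. One would record an event dated before discharge. The other would censor on the day after discharge. The first dataset counts as a success someone whom the investigator records as needing oxygen at home, on an endpoint meant to show when oxygen stops. If the choice is left until outcomes are visible, it can no longer be called prespecified.

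**Working it through.** The SAP gives no figure to reproduce here. The check is to apply the two rules, exactly as written, to daily score sequences.

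**Can the sequence 2 then 1.2 occur?** Score 2 is the residual hospitalized category in SAP 5.2.1, assigned when the criteria for 6, 5, 4 and 3 all fail. Two routes lead to it:

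- The participant is off oxygen and the day's lowest SpO2 is above 93%.
- The participant is on oxygen at FiO2 below 50% with a room-air SpO2 above 93%. Score 3 on low-flow oxygen applies only if FiO2 is below 50% "and the participant was not able to sustain a blood oxygen saturation of" more than 93% on room air. Attachment 3 narrows this route: if room-air saturation was not assessed, it is taken as 93% or lower, which gives score 3. A measured room-air value above 93% is therefore needed.

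The 1.1/1.2 split then comes from a different source, the discharge questionnaire. A participant can score 2 through the day of discharge and 1.2 from the day after.

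**Four illustrative sequences.** The days are assumed. All start with score 4 on Days 1–5 and have discharge on Day 12.

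| Sequence from Day 6 | Event rule as written | Rule for discharge on 1.2 | Agree? |
|---|---|---|---|
| 3 (Days 6–9), 2 (10–12), 1.2 (13–28), alive | Event, Day 10 | Censored, Day 12 + 1 = 13 | No |
| 3 (Days 6–12), 1.2 (13–28), alive | No event | Censored, Day 13 | Yes |
| 3 (Days 6–9), 2 (10–12), 1.2 (13–19), death Day 20 | No event (score 6 cancels it) | Censored, Day 28 (death rule) | Yes |
| 3 (Days 6–9), 2 (10–12), 1.1 (13–28), alive | Event, Day 10 | Does not apply | Yes |

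Only the first sequence gives two answers. The conflict is confined to participants alive at Day 28 who score 2, are discharged on 1.2 and have no later score of 3 to 6.

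**With 1.2 added to the deterioration list**, the first sequence has no event and its only outcome is censoring on Day 13. The other three rows do not change.

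**Does another section settle it?** Protocol Section 3 only names the endpoint, and Protocol 9.4.4 only names the test. The worked cases in SAP Attachment 3 show scores as 1, above 1 or missing, without the 1.1/1.2 split. SAP 5.2.3 does state precedence for the primary endpoint: participants who discontinue are censored unless sustained improvement came first. The oxygen endpoint has no such clause.

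**The case against.** The strongest reply is that the sentence on discharge with 1.2 is specific, names the score and allows only death as an exception, so it should be read as governing the general event rule. The primary endpoint supports this: where the SAP wants an earlier event to override censoring, it says so. On that reading there are no false events. This is a fair reading and may be the intended one, but it remains an inference, because the SAP does not state it.

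A reader might go further the other way and infer that these participants are never censored, that the event always wins, and that the log-rank comparison is therefore biased. The documents do not support that. They leave precedence open. Bias would also need the arms to differ in discharge on oxygen, which nothing shows, and its direction would be unknown.

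A reader might also try to size the problem as (number discharged) × (share on 1.2) × (share scoring 2 first). Assuming 40 to 60 of the 111 critical participants discharged, 10–40% of them on oxygen and 20–50% of those scoring 2 first, this runs from 40 × 0.10 × 0.20 = 0.8 to 60 × 0.40 × 0.50 = 12. The documents supply none of the three inputs, and the room-air default in Attachment 3 could push the last share lower. The range illustrates what could happen; it does not estimate it.

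Two further objections stand in part. First, the conflict could also be removed by letting the score-2 event stand and limiting the 1.2 censoring to participants without a prior event. That would be consistent, but it would count people going home on oxygen as having ended it, which fits poorly with the SAP's own exclusion of 1.2 from the event scores. Second, censoring at discharge people known to need oxygen still lets the curve depend on who goes home on oxygen. That is a separate question about the censoring rule, and resolving the contradiction does not answer it.

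**Conclusion.** The contradiction is real and can be seen within a single table entry. One defined group receives both an event date and a later censoring date, with no stated precedence. What follows depends on which rule is programmed: an early false event under the event rule, none under the censoring rule.

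The number affected cannot be estimated from the documents and could be close to zero. Exposure is not limited to the target of about 111 critical participants, because the ITT analysis adds approximately 100 with severe disease. This is one of the other secondary endpoints, tested outside the hierarchy, so primary and key secondary results are unaffected. It should be corrected because the written rules give contradictory results and the correction is nearly free. No material bias has been shown.

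**What to change.** Before unblinding, extend the footnote in SAP 5.4.1 so that the scores counted as deterioration for this endpoint are 1.2, 3, 4, 5 and 6. A score of 2 followed by discharge on oxygen is then not an event, and these participants follow only the existing 1.2 rule (censoring the day after discharge, or at Day 28 if they die by then). If the sponsor prefers the score-2 event to stand, the SAP should say so and restrict the 1.2 rule to participants without a prior event.

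The cost is one addition to the SAP text and one line of derivation code. Compared with a derivation that let the event prevail, the event count may fall slightly.
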